6.6. Supplementary materials and equipment.....	24
6.7. Monitoring Plan	24
7. Statistical considerations.....	25
7.1. Statistical design, method and analytical procedures	25
7.2. Sample size.....	25
7.3. Level of significance and power.....	27
7.4. Drop-out	27
7.5. Pass/fail criteria	27

7.6. Interim analysis	27
7.7. Statistical reason for termination of investigation	27
7.8. Deviation(s) from statistical plan	27
8. Data management.....	27
8.1. Data review, database cleaning, and issuing and resolving data queries	27
8.2. Verification, validation and securing of electronic clinical data systems	27
8.3. Data retention	28
9. Amendments to the CIP.....	28
10. Clinical Investigation Plan deviations.....	28
11. Device Accountability.....	29
12. Statement of compliance.....	29
12.1. Ethics committee and regulatory authorities	30
12.2. Data protection	30
12.3. Indemnity	30
12.4. Financial conditions	30
13. Informed consent process	31
14. Adverse events, serious adverse events and device deficiencies	32
14.1. Adverse events	32
14.2. Device deficiency	32
14.3. Serious adverse events	32
14.4. Medical care of subjects	33
14.5. Reporting and timelines	33
15. Suspension or premature termination of the clinical investigation	34
16. Clinical investigation report.....	34
17. Publication policy	35
18. Bibliography	35

> SYNOPSIS OF THE CLINICAL INVESTIGATION

Objective

The primary objective of the investigation is to obtain indications that the intermittent catheters [REDACTED] can be used to void and empty the bladder

Primary end point and secondary end point(s)

The primary endpoint is: Urine flow rate

The secondary endpoints are: Post void residual urine, haematuria (macroscopic and microscopic) and adverse events.

Explorative endpoints are: Overall discomfort during catheterisation, discomfort during insertion, discomfort during withdrawal, discomfort during urination post catheterisation and handling during catheterisation.

Pass/fail criteria

No formal success criteria are applied in this explorative investigation. The investigation will provide valuable insight into both performance and acceptance of three new intermittent catheters [REDACTED]

Design of the investigation

The study is a single blinded, randomised, cross-over study [REDACTED]

- Part A evaluates two prototypes of intermittent catheters compared to the standard catheter Speed-iCath® Flex in randomised order (Test visit 1-3)

In the investigation ten healthy males will be included. The subjects will be catheterised once per visit. During the test visits the primary, secondary and explorative endpoints will be registered. The visits will be conducted at Coloplast A/S, [name].

Subjects will be asked to participate in an interview in continuation of their last visit for part A (Test Visit 3 [REDACTED]). The interviews will be performed by a Coloplast representative asking questions related to their experience with the catheter. In addition, a Coloplast representative will interview the Investigator and her representatives after LPO with questions related to their experience with the catheters.

The investigation is planned to be conducted in August 2018-January 2019. The visit window will be minimum five days between the visits (catheterisations), to ensure time for healing of any potential urethral trauma. [REDACTED]. However, the maximum time between visits should be adjusted to ensure the subject is terminated before LPO.

Population

Inclusion criteria	Exclusion criteria
Has given written informed consent and signed letter of authority	Has a previous history of genitourinary disease including congenital abnormalities and surgical procedures performed in the urinary tract
Is at least 18 years of age and has full legal capacity	Has symptoms of urinary tract infections (frequent urination, stinging and pain at urination)
Is a male	Are participating in any other clinical investigation related to urinary tract system during this investigation (inclusion to termination)

Willing to comply without using analgetica¹ up to 24 hours prior to catheterisation visits

Has a negative urine multistix for erythrocytes (microscopic haematuria), leukocytes and nitrite

Known hypersensitivity toward any of the test products

Haematuria is an explorative end point. If subjects have haematuria when entering the investigation, it could affect the evaluation of data. Haematuria could also be a sign of Urine Tract Infections (UTI) which is also an exclusion criterion

Test products

The investigational devices are intermittent catheters for single use only and are intended to be used for drainage of the bladder through the urethra. The test products will be similar to the CE marked SpeediCath® Flex catheter (comparator) with a few exemptions in the raw catheter, see section 2.1.4.

Investigation approval

The investigation will be approved by the Ethical Committee in Denmark and the Danish Medicines Agency before investigation initiation.

1. List of personnel involved in the Investigation

[figure not shown]

1.3. Other

All delegated tasks from Investigator to Study Nurses will be documented in the Site Personnel Signature and Delegation List.

2. Identification and description of the investigational device

The investigational devices are intermittent catheters for single use only and are intended to be used for drainage of the bladder through the urethra. The investigational catheter devices are similar to the CE marked SpeediCath® Flex, with a few exemptions in the raw catheter, see section 2.1.4. [REDACTED]

[REDACTED]

[REDACTED]

2.1. Manufacture

The investigational device [REDACTED] will be manufactured by:

Coloplast A/S
[name]
[name]
Denmark

2.1.1. Identification, traceability and labelling of device

The investigational catheter devices (Test product 2 and 3) [REDACTED] will be labeled as shown in figure 1. SpeediCath® Flex used in CP290 is already CE marked and is labelled accordingly. The investigation will only be conducted in Denmark, therefore the labels are only printed in Danish.

Figure 1: Labelling for the investigational catheter devices (Test product 2 and 3) [REDACTED]

*Will be adjusted according to the type of test product. ** Will be adjusted according to the lot.

2.1.2. Clinical investigation purpose of device

The investigation test devices (Test product 2 and 3) are intended for transient (less than 60 minutes) intermittent drainage of the bladder. [REDACTED]

The test devices are indicated for drainage from the bladder through the urethra in healthy male volunteers. There are no proposed contraindications.

2.1.3. Intended population for the device

The intended population for the devices are healthy male volunteers.

2.1.4. Description of investigational device

Intermittent Catheters (Figure 2)

The investigational catheter devices are for single use only and are intended to be used for drainage of the bladder through the urethra. The products are intended to be used by healthcare professionals on healthy volunteers in the clinical investigation CP290.

The investigational catheter tubes will be similar to the CE marked SpeediCath® Flex with a few exemptions in the raw catheter. [REDACTED]

The remaining parts of the investigational catheter devices are identical. All materials used for the investigational catheter devices are identical to the already CE marked SpeediCath® Flex.

The investigational catheters (Test Product 2 and 3) and Comparator (SpeediCath® Flex) are classified as class I sterile device [REDACTED] according to the Medical Device Directive, MDD 93/42/EEC, Rule 5. [REDACTED]

[figure not shown]
[figure not shown]

Figure 2: Illustration of SpeediCath® Flex and Test products 2 and 3 (raw catheters).

2.1.5. Handling and training

The handling of the test products [REDACTED]. The test products are to be handled in the same way as the comparator which the study nurse is experienced in using.

The investigational device (catheters) are for single use. The IFU consists the warning: "Reuse of this single use product may create a potential risk to the user. Reprocessing, cleaning, disinfection and sterilisation may compromise product characteristics which in turn create an additional risk of physical harm to or infection of the user".

Products should be stored at room temperature and away from direct sunlight, which described in the labelling.

[REDACTED]

For further details, please see the Investigators Brochure.

2.1.6. Comparator product

The CE-marked Standard SpeediCath® Flex (Nelaton, CH12) will be used as comparator in this investigation. As the comparator product is already on the market and will be used within the intended use in this clinical investigation, it is not considered an investigational device per ISO 14155:2011 and is thus not described here. Please refer to the ISO 14155:2011 for details.

3. Justification for the conduct of the clinical investigation

Intermittent catheterisation is the preferred method of bladder emptying for persons with spinal cord injuries and neurogenic bladder dysfunction. Coloplast A/S manufactures different catheters for intermittent catheterisation and works continuously to improve them.

The newly developed prototypes have not previously been evaluated in the human urethra and a clinical investigation is required to demonstrate performance and acceptance.

4. Investigational device and clinical investigation risks and benefits

The clinical investigation is conducted in accordance with current law and applicable standards, see section 12. The rights, safety and well-being of human subjects shall prevail over interest of science of society.

The clinical investigation is conducted in accordance with "The Declaration of Helsinki, 1964, last amended at the 64th WMA General Assembly, Brazil, October 2013".

4.1. Anticipated benefits

By participating in this investigation, the subjects will contribute with important information for developing new intermittent catheters [REDACTED], that in turn may benefit individuals who are dependent on catheters for emptying their bladder.

4.2. Anticipated risks, side effects and disadvantages

Risks associated with the investigation may be discomfort or stinging in the urethra during the catheterisation. Furthermore, there may be a risk of micro trauma and haematuria after catheterisation, which heals within 1-3 days. The test catheter is not expected to produce more stinging or discomfort compared to any other standard catheter on the market.

Possible interactions with concomitant medical treatments

There is no known interaction between the use of catheters and concomitant medication. However, the use of analgesics must be avoided up to 24 hours prior to catheterisation visits during this investigation, since pain relief could affect primary an explorative endpoints and general experience of catheterisation.

Steps that will be taken to control or mitigate the risks

All subjects are encouraged to contact the investigator in case of problems or unwanted side effects. During the investigation, all subjects will be enquired about their health and eventual problems (including issues mentioned here) by the investigator or representative at every visit. In addition, trained health professionals will perform the catheterisations.

Risk-to-benefit rationale

The risk and disadvantage of participating in the investigation are estimated to be low. The healthy volunteers will not have any benefits from this investigation, but catheter users may in the future benefit from a new and improved catheter and methods for faster voiding.

5. Objectives and hypotheses of the clinical investigation

5.1. Objective

The primary objective of the investigation is to obtain indications that the intermittent catheters [REDACTED] can be used to void and empty the bladder.

5.2. Hypotheses

It is hypothesised that the catheters with the new design increase urine flow rate and/or reduce post void residual urine compared with the CE-marked SpeediCath® Flex without worsening overall discomfort during catheterisation.

6. Design of the clinical investigation

Table 1: Overview of the design of the investigation. The investigation is single blinded, cross-over, randomised divided into two parts; Part A and Part B.

Visit		Days to next visit
Information visit	Oral and written information about the investigation	
Inclusion visit (V0)	Inclusion	
Part A		
Test Visit 1 (V1)	Catheterisation with randomised product 1	≥ five days
Test Visit 2 (V2)	Catheterisation with randomised product 2	≥ five days
Test Visit 3 (V3)	Catheterisation with randomised product 3	≥ five days

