6.4.4. Flow-chart

Table 4 chart showing the connection between visits and assessments.

	PERFORMED BY	SOURCE	INFORMATION AND INCLUSION VISIT 0	VISIT 1-3	VISIT 5-6	TERMINATION VISIT
General						
Oral information	Investigator	NA	X			
Written informed consent	Subject	Informed consent form	X			
Signed Letter of authority	Investigator	Letter of Authority Form	X			
Consent to interview	Subject	Informed consent form - Interview	X			
Check of in- and exclusion criteria	Investigator	CRF	X			
Allocation to subject number	Investigator	CRF	X			
Randomisation	Investigator	Randomisation Envelope	X			
Insurance of subjects well-being and compliance with CIP	Investigator	CRF	X	X	X	X
Registration of Demographic						
Date of birth	Investigator	CRF	X			
Check for symptoms of UTI, damage to urine tract system and use of analgesics before catheterisation						
Urine sample from subject	Subject	NA		X	X	
Leukocytes (urine dipstick)	Investigator	CRF		X	X	
Nitrite (urine dipstick)	Investigator	CRF		X	X	
Haematuria – microscopic (urine dipstick - erythrocytes)	Investigator	CRF		X	X	
Check for use of analgesics 24 hours before catheterisation	Investigator	CRF		X	X	
Catheterisation per randomisation	Investigator	CRF		X	X	
Registration/measurement of primary end points – during catheterisation						
Urine flow rate - Max flow ($\frac{ml}{s}$) - Middle flow ($\frac{ml}{s}$)	Investigator	CRF (or possible printed graph)		X	X	
Registration/measurement of secondary end points - after catheterisation						
Post void residual urine	Investigator	CRF (or possible print)		X	X	
Haematuria – macroscopic (visible blood)	Investigator	CRF		X	X	
Urine sample from subject	Subject	NA		X	X	
Haematuria – microscopic (urine dipstick)	Investigator	CRF		X	X	
AEs/ADEs/SAEs/SADEs	Investigator	CRF		X	X	X
Registration of explorative end points						
Overall discomfort during catheterisation	Subject	CRF		X	X	X
Discomfort during insertion	Subject	CRF		X	X	

Discomfort during withdrawal	Subject	CRF		X	X	
Discomfort during urination post catheterisation	Subject	CRF		X	X	
Handling during insertion	Investigator	CRF		X	X	
Handling during withdrawal	Investigator	CRF		X	X	
Handling during insertion	Investigator	CRF		X	X	
Handling during catheterisation	Investigator	CRF		X	X	
Interview	Coloplast representative	Interview notes		V3	V6	
Urine flow - Micturition time (sec) - Flow time (sec) [REDACTED] - Micturition volume (ml)	Investigator	CRF (or possible printed graph)		X	X	
Registration of termination						

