6.4.6. Blinding

During the investigation, the subject will be blinded with a curtain so he will not be able to see which catheter is used. The nurse is not blinded as it is not possible to blind the products due to visible differences. It is a disadvantage that it is not possible to blind the nurses as there could be some bias in their assessment of the products tested. However, it is the subject who assesses the secondary end points regarding discomfort (VAS) during catheterisation and micturition.

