6.4.7. Case Report Forms

All assessments and observations throughout the investigation for each subject must be carefully recorded in the CRF. The CRFs are printed and supplied by Sponsor. A CRF is provided for each subject. It is the responsibility of the Investigator that all data are entered promptly and correctly. Each CRF have printed instructions for completion.

The CRF for each subject will be divided in two parts; one for the investigator or representative to complete (Investigator Binder) and one for the subjects two complete (Subject Binder). The study personnel will be responsible for guiding the subject on how to complete the subject's part of the CRF. The CRF will clearly state which parts are to be completed by whom. The subject's part will be the pages regarding discomfort during insertion and withdrawal of the catheter measured by the VAS-scale. These pages will be in Danish. After

completion by subject, the study nurse or investigator will measure the VAS-scale and write the measurement in the CRF.

The sponsor will be responsible for training the investigator and the investigation personnel in completion of the CRF. Only personnel who have signed the Site Personnel Signature and Delegation Log and the Clinical Investigation Training Log will fill in the Investigator Binder.

It will be the responsibility of investigator that all measurements and observations are correctly noted with a pen (permanent writing utensil) in the CRF.

Any correction in the CRF must be clearly signed and dated by authorised site personnel. The entry corrected must be crossed out so that the entry is still legible.

Example 1:

2010-11 PLN

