7.1. Statistical design, method and analytical procedures

Design

The study is a single blinded, randomised, crossover study divided into two parts; Part A and Part B.

- Part A evaluates 2 prototypes of intermittent catheters compared to a standard SpeediCath® Flex catheter.

Populations

Intention to Treat (ITT) and Safety populations will be defined at a formal data review meeting just before database lock. As a minimum, the clinical manager and the statistician will be involved in the classification of subjects.

The **ITT population** will be constituted by all randomised subjects with valid informed consent who have been exposed to at least one product, and with valid information on at least one product with respect to either primary or secondary endpoints. Any exclusion of subjects from the ITT set beyond this must be separately documented.

The **Safety population** (basis for AE summary) will be constituted by subjects that have given informed consent and have been exposed to at least one product.

A formal PP population is not planned due to the explorative nature of the investigation. Considering the data obtained it might however be considered to make additional explorative analyses based on a subset of the ITT population.

Individual endpoints/data points may be excluded from analysis, even though the corresponding subject belongs to the ITT population. This could for example be due to protocol violations at one test day that would affect the primary endpoint at the corresponding test day, but have no impact on the primary endpoint on the remaining test days. Any exclusion of endpoints/data points will be documented.

General

All efficacy will be based upon the ITT (intention to treat) population and adverse events will be summarized based on the safety population.

If data is represented by a curve (e.g. pressure and force), relevant characteristics of the curve (e.g. peak of the curve) will be summarised and/or listed.

Where meaningful, data will be summarised and/or listed. Additional explorative post-hoc analyses can be performed if deemed relevant.

Primary endpoint

A mixed model, for part A and B respectively, with subject included as a random component will be applied for the primary analysis of the urine flow rate.

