Treatment (SpeediCath® Flex, test product 2, test product 3 (part A) and SpeediCath® Flex catheter and Test product 2 (part B) [REDACTED]) and Day of catheterisation visit (1, 2, 3, 5 and 6) will be included as fixed effects with age as a covariate. The contrast between the catheters as well as the 95% confidence intervals will be estimated using Proc Mixed in SAS.

Secondary endpoints

Discomfort, measured on a VAS scale and post void residual urine will be analysed using a linear mixed model, for part A and B respectively, same as described in the primary endpoint

Adverse events will be summarised and/or listed based on the safety population.

Haematuria data will be listed.

The odds ratio between the test products as well as the corresponding 95% confidence intervals will be estimated.

All statistical analyses will be made with SAS version 9.4 (SAS Institute Inc., Cary, NC).

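### Does the plan leave the variables behind its section 5.2 hypothesis too loosely defined to analyse?

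*Combined protocol and SAP*

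**What the plan says.** **Hypothesis.** Section 5.2 expects the new designs to "increase urine flow rate and/or reduce post void residual urine compared with the CE-marked SpeediCath® Flex without worsening overall discomfort during catheterisation".

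**Flow.** The Synopsis gives one primary endpoint, urine flow rate. In the flow-chart (6.4.4) the row under the primary endpoints begins "Urine flow rate - Max flow" and goes on to middle flow, both in ml/s. Section 7.1 says a mixed model with a random subject effect "will be applied for the primary analysis of the urine flow rate". It adds treatment and visit day as fixed effects and age as a covariate, and states: "The contrast between the catheters as well as the 95% confidence intervals will be estimated using Proc Mixed in SAS".

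**Discomfort.** The Synopsis reads: "Explorative endpoints are: Overall discomfort during catheterisation, discomfort during insertion, discomfort during withdrawal", followed by discomfort at later urination and handling. Sections 6.1.1 and 6.4.4 use the same tier. Section 7.1, under its secondary endpoints heading, says: "Discomfort, measured on a VAS scale and post void residual urine will be analysed using a linear mixed model", on the same terms as the primary model. Section 6.4.6 answers the lack of nurse blinding by noting that "it is the subject who assesses the secondary end points regarding discomfort (VAS" scale). Section 6.4.7 describes the subject's part of the CRF as the "pages regarding discomfort during insertion and withdrawal of the catheter measured by the VAS-scale".

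**Status of the study.** Section 5.1 seeks indications only, 7.2 reports no formal sample size calculation, 7.3 sets two-sided 5% tests, and 7.5 applies no success criteria.

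**The concern.** Read strictly, three parts of the hypothesis look open.

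- **Primary outcome.** If only one flow measure is meant to be primary, two analysts could fit the same model to different variables and report different primary results. The choice could also be made after the data are seen.
- **Discomfort.** It carries two tier labels. The CRF summary in 6.4.7 might mean that the item named in 5.2 is never collected. Under the Synopsis tiers, the flow-chart has no secondary endpoint performed by the subject apart from supplying a urine sample, so the blinding argument in 6.4.6 appears to lose its footing.
- **Without worsening.** An interval is planned, but nothing says how it answers this condition. With ten men, a non-significant difference could be mistaken for evidence that discomfort is no worse.

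**Working it through.** The plan gives no effect size, SD, power or margin, so its ten subjects cannot be re-derived. The check compares the sections and then sizes what is left open.

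**1. Which discomfort variable?** Section 5.2 specifies overall discomfort during catheterisation. That is the name of one endpoint in the Synopsis, 6.1.1 and 6.4.4. The model in 7.1 is for discomfort on a VAS scale, which covers all four VAS items. The item that answers 5.2 is therefore identified.

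**2. Is it collected?** Section 6.1.1 contains the wording of the VAS question on the overall catheterisation. Section 6.4.1 has the subject register the VAS discomfort endpoints at each test visit. The flow-chart lists overall discomfort with the subject as performer and the CRF as source, at visits 1-3 and 5-6. Against these stands one summary sentence in 6.4.7, which also omits discomfort at later urination. It reads as loose description.

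**3. Does the tier matter?** The label would matter if it set the model, the error rate or a decision. The model is stated in 7.1 whichever tier applies. There is no testing hierarchy, and 7.5 has no success rule. The argument in 6.4.6 depends on who scores discomfort (the subject, behind a curtain) and not on the word secondary.

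**4. How wide is the discomfort interval?** Part A has 10 men and 3 periods. With subject, treatment and visit day fitted, residual df = 30 - 1 - 9 - 2 - 2 = 16.

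Half-width = t(0.975, 16) × √(2/10) × SD = 2.120 × 0.447 × SD = 0.948 within-subject SD. With nine men (14 df): 2.145 × √(2/9) = 1.011 SD.

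| Assumed within-subject SD (cm) | 95% half-width, ten men (cm) |
|---|---|
| 1.0 | 0.95 |
| 1.5 | 1.42 |
| 2.0 | 1.90 |

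The interval is wide. The planned analysis reports it, so the reader will see how much worsening the data cannot exclude.

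**5. How often would max and middle flow disagree?** Assumptions (the documents give none): the same true effect on both measures, in within-subject SD units, and within-subject errors correlated 0.5 to 0.9. Simulation: 40,000 trials per setting, 10 men × 3 periods, subject + period + treatment model, two-sided 5%. Age is constant within a man and does not affect these contrasts.

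| True effect (SD) | Power, one measure | Disagree on p < 0.05, one prototype contrast |
|---|---|---|
| 0 | – | 4–8% |
| 0.5 | 18% | 10–22% |
| 0.75 | 35% | 14–32% |
| 1.0 | 56% | 15–34% |
| 1.5 | 88% | 7–16% |
| 2.0 | 99% | 1–2% |

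The low end of each range is correlation 0.9 and the high end 0.5. For at least one of the two prototype contrasts, disagreement is 25–50% at 0.75 SD and 27–54% at 1.0 SD.

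Disagreement is greatest where one measure has power near one half and falls on either side. With no effect, the chance that at least one of the two measures is significant for one contrast is 1 - 0.95² = 9.75% if they are independent, and about 9.1%, 7.8% and 7.1% at correlations 0.5, 0.8 and 0.9, against 5% for a single measure.

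**The case for a change.** The strongest case for a change is the primary flow variable. A plan that names a primary endpoint, a directional hypothesis, 5% tests and a primary analysis ought to let someone else reproduce that analysis, even in an exploratory study. The investigator is employed by the sponsor (12.4), and results will be posted publicly (section 17). Saying whether one or both measures are primary would cost a sentence, although as an endpoint change it would go through section 9.

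The factual part stands: 7.1 names neither measure, and its sentence on the outcome shows no redaction. The consequence is weaker. Sections 6.1.1 and 6.4.4 head the row in the plural, and 6.4.4 lists both measures together, so modelling and reporting both is a natural reading. The plural is only modest support, since the other tiers use it too and the Synopsis uses the singular. The primary row of 6.1.1 may also have lost text in extraction.

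The caution about p > 0.05 is also sound: if no significant worsening were read as success, a true worsening of 1 SD would be missed 44% of the time, and one of 0.5 SD 82% of the time. But no section proposes that reading, and the caution applies to any small study.

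**Conclusion.** No change to the plan is needed. The open choice of flow measure is a gap that an analyst fills sensibly by applying the stated model to both recorded measures and showing both sets of estimates and intervals. The tier labels in 6.4.6 and 7.1 and the short CRF description in 6.4.7 are clerical inconsistencies. Section 5.2 identifies its discomfort variable, and the flow-chart shows it being collected. Post void residual urine, the remaining variable in the hypothesis, is a single measure in ml and consistently secondary.

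The largest quantified effect is a 14 to 34% chance that the two flow measures fall on opposite sides of p = 0.05 for one contrast, near the effect sizes where that chance peaks. It rests on assumed correlations and effect sizes. No stated figure or error rate is wrong, and no decision turns on a p-value, because there is no success criterion and contrasts are reported with 95% intervals. The conclusion would differ in a confirmatory trial, where the choice of primary variable would carry the type I error.
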